# **5.5** Maintenance Phase: (see also section 6.2.2, Tables 7, 8)

Please note that any patient with residual disease (with at least PR) may move onto maintenance regardless of blood counts.

Patients who enter a maintenance phase require platelets  $\geq 50 \ge 10^{9}/L$  and an ANC  $\geq 1.0 \ge 10^{9}/L$ . If a subject presents with a Grade 4 cytopenia for more than 1 week during Maintenance phase, unless it is thought to be due to the underlying disease, venetoclax dosing should be interrupted until platelets  $\geq 50 \ge 10^{9}/L$  and ANC  $\geq 1.0 \ge 10^{9}/L$ .

During Maintenance, for subjects, in CR/CRi, receiving venetoclax who required >1 interruption or delay of study drug administration for grade 4 cytopenias, venetoclax, at dose prescribed for that cohort, should be administered for 21 days out of 28 days during each of the subsequent cycles. If, despite these modifications, a subject continues to have persistent grade 4 cytopenias, venetoclax should be administered for 14 days out of 28 days during each of the subsequent cycles.

If grade 3 cytopenias (i.e., ANC <  $1.0 \times 10^9$ /L and/or platelets <  $50 \times 10^9$ /L) persist please discuss with PI, however those who still continue to have a grade 4 cytopenia should be taken off study.

Venetoclax therapy will be continued daily at the previously assigned dose for as long as patients continue to benefit or until disease progression or unacceptable toxicity.

Patients who enter the maintenance phase in partial remission should have a bone marrow assessment after the first month of maintenance therapy (cycle 3). Those with an improved response should continue with maintenance Venetoclax. Those with stable disease should continue treatment if the drug is well-tolerated and if the primary hematologist believes that Venetoclax is of benefit. If there is disease progression, patients should be taken off study.

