# Table 7. Dose Duration Reduction for Venetoclax Toxicity (Maintenance)

There will be no dose reductions of Venetoclax for hematologic toxicity during cycles 1 and 2. Patients who are in CRi after either cycle may temporarily discontinue Venetoclax for up to four weeks to allow for platelet or ANC recovery. Patients who enter the maintenance phase must have platelets  $\geq 50 \times 10^9/L$  and an ANC  $\geq 1.0 \times 10^9/L$ 

If a dose reduction is required, please follow the guidelines in Table 7. Missed Venetoclax doses are not to be made up.

Toxicity	Occurrence	Action					
Tumor Lysis Syndrome (TLS)							
TLS defined by the Cairo-Bishop criteria; see Appendix IV	Any	Implement standard TLS treatment (increase IVF). Withhold Venetoclax if TLS labs do not improve by 25% within 24 hours. Resume once TLS labs improve.					
Non-Hema	atologic Toxicities	s (Consolidation and Maintenance only)					
toxicities 2 nd and		Withhold Venetoclax. Once the toxicity has resolved to Grade 1 or baseline, resume at same dose.					
		Withhold Venetoclax. Once the toxicity has resolved to Grade 1 or baseline, resume at a reduced dosing duration (see Table 7).					
	Hematologic To	oxicities (Maintenance only)					
Grade 4 neutropenia with or without fever; or Grade 4 thrombocytopenia	1 st occurrence	Interrupt Venetoclax. To reduce infection risks associated with neutropenia, G-CSF may be administered if clinically indicated, provided there is bone marrow confirmation of leukemia clearance. Once the toxicity has resolved to Grade 2 or baseline, resume at the same dose duration (Table 7).					
	2 nd occurrence	Interrupt Venetoclax. Consider using G-CSF as clinically indicated. Once the toxicity has resolved to Grade 2 or baseline, follow dose duration reduction guidelines (Table 7).					

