# Table 8. Venetoclax Dosing Regimen Modifications

3rd and subsequent occurrencesInterrupt Venetoclax. Consider using G-CSF as clinically indicated. If toxicity remains at grade 3, may discuss with PI regarding treatment options. If grade 4 toxicity persists, remove from study (Table 7).
--

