#### Consider discontinuing Venetoclax if toxicities recur despite two dose duration reductions

# 6.3 **Protocol Therapy Discontinuation**

In addition to discontinuation due to therapy-related toxicities as outlined in section **6.1**, a subject will also be discontinued from protocol therapy and then followed up per protocol under the circumstances outlined below. The reason for discontinuation of protocol therapy will be documented on the electronic case report form (eCRF) and should also be discussed with the study sponsor-investigator.

- Documented disease progression
- Unacceptable toxicity
- The treating physician believes a change of therapy would be in the best interest of the subject
- Follow-up bone marrow biopsy demonstrates either significant residual leukemic blasts or significant cytoreduction with a high percentage residual leukemic blasts, but BM study is deemed by the hematopathologist to demonstrate less than a partial response.
- Bone marrow biopsy during maintenance phase shows stable disease but the treating hematologist believes that the Venetoclax is no longer of benefit.
- DLT as defined above or if there is grade 3 neutropenia or thrombocytopenia after holding Venetoclax for four weeks at the end of cycles 1 or 2
- Patient is unable to comply with protocol requirements
- The subject requests to discontinue protocol therapy, whether due to unacceptable toxicity or for other reasons. If a subject decides to prematurely discontinue protocol therapy ("refuses treatment"), the subject should be asked if he or she may still be contacted for further scheduled study assessments. The outcome of that discussion should be documented in both the medical records and in the eCRF.
- A female subject becomes pregnant
- Development of a second malignancy (except for basal cell carcinoma or squamous cell carcinoma of the skin) that requires treatment which would interfere with this study.
- If protocol therapy is interrupted for  $\geq 30$  days.
- Lost to follow up. If a research subject cannot be located to document survival, the subject may be considered "lost to follow-up." All attempts to contact the subject must be documented.

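### Section 5.5, Table 7 and Table 8 do not match on grade 4 cytopenia in maintenance: the trigger for interruption, the third-occurrence step and the force of the last step all need reconciling

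*Combined protocol and SAP*

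**What the plan says.** Section 5.5 sets its trigger at "Grade 4 cytopenia for more than 1 week during Maintenance phase" and adds an exemption and a hold: "unless it is thought to be due to the underlying disease, venetoclax dosing should be interrupted until platelets" and neutrophils reach stated thresholds (platelets at least 50 × 10⁹/L, ANC at least 1.0 × 10⁹/L). Patients in CR/CRi "who required >1 interruption or delay of study drug administration for grade 4 cytopenias" go to 21 of 28 days. The next step is that if "a subject continues to have persistent grade 4 cytopenias, venetoclax should be administered for 14 days out of 28 days". Section 5.5 then refers persisting grade 3 cytopenia to the PI and takes patients with continuing grade 4 cytopenia off study.

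Table 7 counts venetoclax toxicity events. The schedule stays at 28 days after the first, falls to 21 after the second and to 14 after the third, and the fourth means discontinuation.

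The hematologic rows of Table 8 apply to "Grade 4 neutropenia with or without fever; or Grade 4 thrombocytopenia". The first occurrence is interrupt and resume at the same duration. The second is interrupt and shorten according to Table 7. For the third and later occurrences the row says to interrupt, to discuss with the PI if grade 3 remains, and "If grade 4 toxicity persists, remove from study (Table 7").

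The line after Table 8, just before Section 6.3, reads "Consider discontinuing Venetoclax if toxicities recur despite two dose duration reductions".

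These passages apply together. The heading of 5.5 refers to 6.2.2 and both tables, and 5.4 says twice that the maintenance rules in 6.2.2 apply. None is given precedence.

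**The concern.** Sites in a multicenter study can each follow the protocol and still handle the same severe cytopenia differently. The trigger carries the most weight, because it decides whether dosing is held and also whether the episode counts as an event that moves the patient down the 28, 21, 14-day sequence. At stake are consistent safety handling across sites and the meaning of the summaries in Section 12.6.3, which report holds, reductions, discontinuations and dose intensity by dose level. With only a few patients per dose level, differences in which passage was followed could be mistaken for differences between doses.

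**Working it through.** The plan gives no figure to reproduce. The check applies each rule to the same episode. It assumes that an event in Table 7 is an occurrence in Table 8, which the protocol does not state.

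| Grade 4 episode in maintenance | Section 5.5 | Tables 7 and 8 | Match? |
|---|---|---|---|
| First, over 1 week, not disease-related | Interrupt, resume 28/28 | Interrupt, resume 28/28 | Yes |
| First, 1 week or less | No interruption called for | Interrupt, resume 28/28 | No |
| Any, thought disease-related | No interruption called for | Interrupt | No |
| Second, over 1 week, not disease-related, CR/CRi | Interrupt, 21/28 | Interrupt, 21/28 | Yes |
| Second, same, but PR | Interrupt, no shortening rule | Interrupt, 21/28 | No |
| Second, 1 week or less | No interruption called for | Interrupt, 21/28 | No |
| Third, over 1 week, not disease-related, CR/CRi | 14/28; off study if grade 4 still continues | Table 7: 14/28. Table 8: interrupt, remove if grade 4 persists, 14-day step not stated | Unclear |
| Fourth | Off study if grade 4 still continues | Table 7: discontinue. Table 8: remove if grade 4 persists. Line after Table 8: consider discontinuing | No |

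Scheduled dosing days at each step:

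- 28/28 = 100%
- 21/28 = 75%
- 14/28 = 50%
- stopped = 0%

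**Trigger.** Take a CR/CRi patient with one episode of a week or less and then one of more than a week, neither disease-related. Section 5.5 counts one interruption, so the schedule stays at 28/28 (100%). The tables count two events, so it becomes 21/28 (75%). If four successive episodes all last a week or less, 5.5 leaves the schedule at 100% throughout. The tables give 100%, 75%, 50% and then discontinuation. The study calendar schedules maintenance blood counts on days 1 and 15, so scheduled tests alone may not show whether an episode exceeded a week.

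**Third occurrence.** The Table 8 row gives no resumption threshold and does not define when toxicity persists. It cites Table 7 for removal from study, but Table 7 shortens to 14 days at the third event and discontinues only at the fourth.

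**Last step.** After 28 to 21 and 21 to 14, two reductions have been made. The next event is a discontinuation in Table 7 and only a matter for consideration in the line after Table 8. The terms differ too: Table 7 discontinues, while 5.5 and Table 8 take the patient off study. Section 6.3 separates stopping protocol therapy from withdrawing from the study.

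**Recovery threshold.** By 5.5's own gloss, grade 3 means ANC below 1.0 or platelets below 50 × 10⁹/L. Its threshold therefore corresponds to the grade 2 limb of Table 8. The two part only on Table 8's alternative of return to baseline. That matters for patients with residual disease, who may enter maintenance regardless of counts.

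**The case against.** The strongest defence is that the passages are meant to be read together and mostly can be. Interrupting and shortening are largely successive steps. Section 5.5 says when to interrupt and does not forbid an earlier hold, so continuing through a short episode is implied and not instructed. The third-occurrence row of Table 8 also covers later occurrences, so it spans Table 7's third and fourth events. A coherent reading is available: interrupt, go to 14 days if counts recover, remove if grade 4 does not resolve. Section 6.3 also ends protocol therapy after an interruption of 30 days or more, which limits how long a hold can run.

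Much of this stands. A reader might infer that 5.5 keeps a third-event patient on treatment while Table 8 removes the patient. The documents do not support so flat a contradiction, because 5.5 also takes continuing grade 4 cytopenia off study and its wording nearly matches the last row of Table 8. What remains there is an unstated 14-day step, an undefined condition and an ill-fitting citation. The 30-day limit does not define that condition, and it ends therapy, not study participation.

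The defence does not reach the trigger. One passage sets conditions on duration and cause, the other sets neither, and nothing elsewhere chooses between them.

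**Conclusion.** The point holds as an internal inconsistency in three places: the trigger is a clear conflict, the third-occurrence wording is incomplete, and the last step is mandatory in one place and optional in another. It affects episodes of a week or less, episodes attributed to disease, patients in PR (the shortening rule in 5.5 covers only CR/CRi), and third or later events. Where it applies, scheduled dosing can differ between 100%, 75%, 50% and 0% of days. The number of patients involved cannot be derived from the documents.

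Two wider inferences are tempting. The first is that every maintenance patient with grade 4 cytopenia is affected; two rows of the comparison show full agreement on the action. The second is that survival endpoints or the dose decision are compromised. The DLT definition in 5.2 concerns cycle 1 and count recovery to day 56. Sections 4, 6.3 and 7.2 continue follow-up after treatment stops, so RFS and EFS are little affected, although follow-up without progression is limited to 6 months after treatment is discontinued.

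This is a modest point, worth correcting for consistent safety handling and interpretable exposure summaries. The conclusion rests on reading Table 7 events as Table 8 occurrences and on no precedence being stated.

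**What to change.** Reconcile Section 5.5, Table 7, Table 8 and the line after Table 8 into one sequence, kept in one place and cross-referenced from the others. It should state:

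- the trigger, with or without conditions on duration and cause, and what counts as an event;
- the action at each occurrence, including the third;
- the recovery threshold for resuming, and what it means for toxicity to persist;
- which response groups each step covers;
- whether the last step is mandatory, and whether it means stopping therapy or leaving the study.

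Which rule is right is for the sponsor to decide. The cost is protocol wording in one amendment, with no extra patients or visits from the reconciliation itself. If maintenance data already exist, the exposure summaries should say which rule was applied to each hold or reduction.

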# 5.6 Transplant-eligible Patients

Patients deemed suitable for transplant may be removed from the study at any point, at the discretion of the treating physician. We suggest a period of 2-3 months between the last dose of Gemtuzumab and the beginning of any HSCT conditioning regimen. In view of the infrequent association of VOD with Gemtuzumab use, we recommend the consideration of alternatives to TBI/TMI-containing protocols, which may increase the risk of VOD, for these patients. Ultimately, the final decision is deferred to the site PI.

# 5.7 **Pre-medication and Hydration**

# Gemtuzumab:

Premedicate with acetaminophen 650 mg orally and diphenhydramine 50 mg orally or intravenously one hour ( $\pm 15$  min) prior to the administration and methylprednisolone 1 mg/kg or an equivalent dose of an alternative corticosteroid within 30 minutes ( $\pm 10$  min) prior to the infusion of GO.

Additional doses of acetaminophen and diphenhydramine may be administered every 4 hours after the initial pretreatment dose. It is advised to repeat the same dose of methylprednisolone or an equivalent corticosteroid for any sign of an infusion reaction (e.g., fever, chills, hypotension or dyspnea) during the infusion or within 4 hours after the initial pretreatment dose.

NOTE: For patients with hyperleukocytosis (leukocyte count greater than 25 x  $10^{9}/L$ ), cytoreduction (hydroxyurea) is required prior to starting treatment.

# Venetoclax:

Venetoclax can cause rapid reduction in tumor thereby increasing the risk for TLS, despite the initial ramp-up phase. To mitigate risk of TLS, patients should receive 1.5 - 2 L hydration (oral or IV) daily in addition to use of a uric acid-lower agent starting at D-2 and continued until physician discretion.

Per the National Comprehensive Cancer Network (NCCN) guideline, Venetoclax is classified as having a minimal to low emetic risk (<30% frequency of emesis). Antiemetic medications for breakthrough nausea will be prescribed at the primary investigator's discretion.

If a patient misses a dose of Venetoclax within 8 hours of the scheduled dose, the patient should take the missed dose and then resume the normal daily dosing schedule. If a dose is missed by more than 8 hours, the patient should not take the missed dose and resume the daily dosing schedule the following day. If a patient vomits after a dose, no additional dose should be taken.

*NOTE:* For patients with hyperleukocytosis (leukocyte count greater than 25 x  $10^{9}/L$ ), cytoreduction (hydroxyurea) is required prior to starting treatment.

# Table 2. Induction (Cycle 1) and Consolidation (Cycle 2) Venetoclax and Gemtuzumab Administration

Drug	Dose 	Route	Schedule	Cycle Length
Venetoclax 	Assigned dose 	Orally	Days 1-28 (Cycle 1: Day -2, -1, 0) 	
Gemtuzumab	$3 \text{ mg/m}^2$	Infusion	Cycle 1 : Days 1, 4, and 7	28 days
	(up to one 4.5 mg vial)		Cycle 2 : Days 1, 4	

Body surface area (BSA) should be recalculated when weight changes by  $\ge 10\%$  according to the Mosteller formula.

Please see Table 1 stepwise ramp-up schema

Venetoclax tablets should be taken orally once daily with a meal and water. Do not chew, crush or break tablets. **NOTE:** Diaries will be provided for self-administration of Venetoclax when subjects are outpatient. On days when both venetoclax and gemtuzumab are given, it is preferred that subjects take venetoclax 1 hour prior to the GO infusion. However, variations from this guidance will not be considered as protocol deviations.

# Table 3. Maintenance Venetoclax Administration (Cycles 3+)

Drug	Dose	Route	Schedule	Cycle Length
Venetoclax 	Assigned dose	Orally	Days 1-28	28 days

Venetoclax tablets should be taken orally once daily with a meal and water. Do not chew, crush or break tablets. **NOTE:** Diaries will be provided for self-administration of Venetoclax when subjects are outpatient.

# 5.8 Concomitant Medications

#### 5.8.1 Allowed Concomitant Medications

All treatments the investigator considers necessary for a subject's welfare may be administered at the discretion of the investigator in keeping with the community standards of medical care.

Appropriate use of transfusions is recommended. Please refer to Supportive Care section for further details.

Due to potential interference of azole antifungals with Venetoclax metabolism, non-azole

antifungals are recommended if antifungal prophylactic medications are used during prolonged episodes of grade 4 neutropenia (Induction phase).

#### 5.8.2 Prohibited Concomitant Medications

Please see Appendix III for a table of prohibited and cautionary medications.

In general, hematopoietic growth factors should not be used unless deemed to be necessary by the treating physician (see also section **5.7**).

#### Strong CYP3A Inhibitors

Venetoclax is predominantly metabolized by CYP3A4/5 therefore concomitant use with strong CYP3A inhibitors (e.g., ketoconazole, conivaptan, clarithromycin, indinavir, itraconazole, lopinavir, ritonavir, ritonavir-boosted nirmatrelvir [Paxlovid], telaprevir, posaconazole, voriconazole) at initiation should be avoided. If use is deemed medically necessary by the treating physician (recognizing that this may increase the risk of tumor lysis syndrome), see Table 4 for dosing instructions. For patients who have completed the ramp-up phase and are on a steady daily dose of Venetoclax, see Table 4 for steady dose instructions – note that Posaconazole requires greater dose reductions than other strong CYP3A inhibitors. If the strong CYP3A inhibitor is discontinued, resume the Venetoclax dose that was used prior to initiating the CYP3A inhibitor 2 to 3 days after discontinuation.

Cohort	Assigned VEN Daily Dose (mg)	Ramp-up day	VEN dose with Posaconazole Daily Dose (mg)	VEN dose with all other strong CYP3A inhibitors Daily Dose (mg)			
		D-2	10	10			
1	100	D-1	10	10			
-1		D0	10	20			
		Steady dose	20	30			
	200	D-2	10	10			
1		D-1	20	20			
1		D0	30	30			
		Steady dose	40	50			
	400	D-2	10	10			
2		D-1	20	20			
2		D0	50	50			
		Steady dose	70	100			
	600	D-2	20	20			
`		D-1	40	50			
3		D0	70	100			
		Steady dose	100	150			

# Table 4: Dose adjustments of Venetoclax in presence of Posaconazole or other strong CYP3A inhibitors

#### Moderate CYP3A inhibitors and P-gp substrates

Avoid use of moderate CYP3A inhibitors (e.g., erythromycin, ciprofloxacin (*not levofloxacin*), diltiazem, dronedarone, fluconazole (>200mg), verapamil). Venetoclax should be administered using caution with substrates or inhibitors of P-gp. Studies indicate that venetoclax may increase the concentration of P-gp substrates. Narrow therapeutic substrates should be administered six hours prior to venetoclax administration. If concurrent use cannot be avoided, reduce the Venetoclax dose by at least 50%. Resume the Venetoclax dose that was used prior to initiating the CYP3A inhibitor 2 to 3 days after discontinuation of the inhibitor.

# CYP3A Inducers

Avoid use of strong CYP3A inducers (e.g., carbamazepine, phenytoin, rifampin, St. John's wort) or moderate CYP3A inducers (e.g., bosentan, efavirenz, etravirine, modafinil, nafcillin).

# 5.9 Supportive Care

Monitoring for tumor lysis is recommended and aggressive hydration and allopurinol prophylaxis should be implemented (see section **5.6**.)

It is recommended that the patient's fluid status and hepatic and renal function and blood glucose levels be carefully monitored during the drug administration period.

Venous Access: A central venous access device is strongly recommended for this study.

Blood Product Support: Appropriate use of all blood products is recommended. Use of cytomegalovirus (CMV) negative products is strongly encouraged for patients documented to be CMV negative and who may later undergo bone marrow transplantation.

Blood products should be irradiated following the current FDA guidelines found at: http://www.fda.gov/cber/gdlns/gamma.html

Hematopoietic Growth Factors: Filgrastim (G-CSF) may be used at the treating physician's discretion, provided bone marrow evaluation demonstrates no evidence of AML, to enhance neutrophil recovery when clinically indicated. The routine use of filgrastim in clinically well patients awaiting count recovery is not recommended.

Prevention of Fungal Infections: Antifungal prophylaxis can reduce morbidity and fungal infection-related mortality in severely neutropenic chemotherapy recipients. Evidence for benefit is strongest for those conditions associated with > 15% rate of systemic fungal infection such as prolonged neutropenia, as observed in AML patients and stem cell transplant (SCT) recipients and is recommended for study patients during Induction. Hospitalized patients who require prophylaxis should receive micafungin, or other non-azole agents (see section **5.8** above).

Management of Fever and Neutropenia: Patients with an ANC  $< 500/\mu$ L (or  $< 1000/\mu$ L and falling) and an oral temperature  $> 38^{\circ}$ C twice in 24 hours or  $> 38.3^{\circ}$ C once, should have empiric systemic antibiotics initiated immediately after appropriate cultures are drawn. The specific choice of empiric antibiotics should be guided by the resistance patterns seen at the individual institution. The antibiotic regimen chosen for febrile neutropenia should contain activity against gramnegative organisms and *Pseudomonas aeruginosa* in particular. Note: aminoglycosides increase the risk of nephrotoxicity.

The persistence of fever for > 3 days despite broad spectrum antibiotic therapy or the emergence of a new fever in a neutropenic patient warrants investigation for invasive fungal infection and initiation of empiric antifungal therapy. Antifungal options include echinocandins (micafungin, capsofungin, and anidulafungin), amphotericin B (or lipid amphotericin products), as well as combination therapy. Azole antifungal medications should be avoided, if possible. The choice of specific agent(s) and length of therapy will be dictated by the suspected or confirmed fungal species, site of infection, and clinical status. Consultation with an Infectious Disease physician is recommended.

